## 9.2.2. Endpoints

### Primary Endpoints:

#### Phase 1

##### **Dose Limiting Toxicity (DLT) for Cytarabine**

For the Phase 1 portion of the study the primary endpoint will be DLT in the determination of the MTD (up to 2 g/m^2 per day) of cytarabine given on Days 8 to 12 following the administration of DACOGEN at 20 mg/m^2 on Days 1 to 5. DLTs are defined as the following

- Hematological DLT will be defined as failure to recover to an absolute neutrophil count (ANC) of  $0.5 \times 10^9/L$  (common terminology criteria for adverse events [CTCAE] Grade 3) and non-transfusion dependent platelet count of  $25 \times 10^9/L$  (CTCAE Grade 3) due to documented bone marrow aplasia/hypoplasia (malignant infiltration or other cause excluded), by Day 42. Bone marrow aplasia/hypoplasia is defined as overall marrow cellularity less than 25%.
- Non-hematological DLT is defined as: any Grade  $\geq 3$  toxicity possibly, probably or definitely related to study drug that persists for  $>5$  days; any Grade 2 toxicity that persists for  $>7$  days and that is intolerable to the patient.

The following events are more likely disease-related and, therefore, not considered DLTs:

- Grade 3 or 4 disseminated intravascular coagulation
- Grade 3 tumor lysis syndrome; grade 3 or 4 fever or grade 3 catheter-related infection, febrile neutropenia, infection, infection with unknown neutrophil count, and infection without neutropenia
- Grade 3 or 4 hypokalemia, hypomagnesemia, hyponatremia, or hypophosphatemia that is related to AML or administration of antifungal medications and is corrected with IV or oral supplementation.

Subjects who do not complete one treatment cycle and do not develop DLT will not be considered evaluable for DLT.

Decitabine PK parameters including  $C_{max}$ , AUC,  $t_{max}$ , and Cl will be determined from blood sampling on Day 5 of Cycle 1 and are a primary endpoint for the Phase 1 portion of the study.

#### Phase 2

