## SAFETY EVALUATIONS

The study will include the following evaluations of safety: adverse events (AEs), clinical laboratory tests (including hematology panel and serum chemistry panel), vital sign measurements (including temperature, heart rate, and blood pressure), physical examinations, and assessment of performance status.

In the Phase 1 portion of the study, the MTD for cytarabine is based on the number of subjects experiencing a dose limiting toxicity (DLT) by the end of Cycle 1. A non-hematological DLT is defined as: any Grade  $\geq 3$  toxicity that persists for  $>5$  days or any Grade 2 toxicity that persists for  $>7$  days and that is intolerable to the

subject. A hematological DLT is defined as Grade 4 neutropenia or thrombocytopenia due to a hypoplastic bone marrow at Day 42, in the absence of malignant infiltration. The nominal duration of each cycle will be 28 days. However, patients who have not experienced bone marrow recovery at Day 28 will be followed up to Day 42. Failure of marrow recovery (improvement to Grade 3) by Day 42 will be considered a DLT. The maximum duration of Cycle 1 will therefore be 42 days.

The decision to escalate or de-escalate cytarabine dose levels and the identification of the MTD will be the responsibility of a Study Evaluation Team (SET) that will convene periodically based on the number of evaluable patients and the occurrence of DLTs. The SET consists of the sponsor's statistician and clinician and other members as needed, eg, clinical pharmacologist, safety physician. The SET will also contain the lead investigator or designee from each country where the study is being conducted.

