##### 3.1.1. Phase 1 Portion of DACOGENAML2004

For the Phase 1 portion of the study, a “rolling 6” design is used. The total number of participants is dependent upon the number of cytarabine dose levels tested; the maximum number of which is 3 dose levels (1 g/m^2, 2 g/m^2, and 1.5 g/m^2) with a maximum of 18 evaluable subjects.

The MTD for cytarabine is based on the number of subjects experiencing a DLT by the end of Cycle 1. A non-hematological DLT is defined as: any Grade  $\geq 3$  toxicity that persists for  $>5$  days or any Grade 2 toxicity that persists for  $>7$  days and that is intolerable to the subject. A hematological DLT is defined as Grade 4 neutropenia or thrombocytopenia due to a hypoplastic bone marrow at Day 42, in the absence of malignant infiltration. The nominal duration of each cycle will be 28 days. However, patients who have not experienced bone marrow recovery at Day 28 will be followed up to Day 42. Failure of marrow recovery (improvement to Grade 3) by Day 42 will be considered a DLT. The maximum duration of Cycle 1 will therefore be 42 days.

The decision to dose escalate from the starting dose of 1 g/m^2 will be based on the number of subjects evaluable and the number pending evaluation during the first cycle. No dose escalation will occur unless a minimum of 3 subjects are fully evaluable with no dose limiting toxicity. If any additional subjects have been treated at that dose level, they must become evaluable before the dose can be escalated. The only exception is the setting in which 5 patients are evaluable, no DLT has been observed and data for one subject is incomplete making it impossible for the MTD to be exceeded. Further details of the “rolling-6” design and the determination of the MTD are provided in Section 6.3.

The decision to escalate or de-escalate dose levels and the identification of the MTD will be the responsibility of a Study Evaluation Team (SET) that will convene periodically based on the number of evaluable patients and the occurrence of dose limiting toxicities. The SET consists of the sponsor’s statistician and clinician and other members as needed, eg, clinical pharmacologist, safety physician. The SET will also include the lead investigator or designee from each country where the study is being conducted. Further description of the SET and their responsibilities is provided in Section 11.9.

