The algorithm counts only subjects who are evaluable or whose data are still pending, ie, subjects who are enrolled but are non-evaluable (do not complete Cycle 1 and do not develop DLT) are not counted. For each dose level, the algorithm starts when 2 subjects have been enrolled. The left portion (3 columns) of Table 3 indicates the current accrual and DLT status; and the right portion depicts the corresponding decisions to be made based on the current dose level. Since the algorithm depends on subjects' status that can change over time, subjects' status as current as possible prior to the next enrollment (or other decision making) should be obtained.

To use the algorithm, a combination of 3 key numbers should be gathered (left 3 columns of **Table 3**): (1) the total number of subjects who have been enrolled at the current dose level minus those who are non-evaluable; (2) the number of subjects who had DLTs; and (3) the number of subjects who have completed Cycle 1, are evaluable, and have no DLT. The

number of subjects whose data are still pending is not essential and hence is not shown in the table.

For example, if 4 subjects have been enrolled at the  $2.0 \text{ g/m}^2$  per day dose level (none is non-evaluable), no DLT has been seen, 3 have completed Cycle 1 (this implies 1 subject with data pending); the 3-number combination in this case would be {4, 0, 3}. Then, shown in right part of the table (light gray shading), the next subject would receive the  $2.0 \text{ g/m}^2$  dose. If 2 subjects have DLTs out of the 4 enrolled, the 3-number combination would be {4, 2, any}. In this case, shown in dark gray shading, the next subject would receive the  $1.5 \text{ g/m}^2$  dose

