**Table 3: Dose Escalation and De-Escalation Algorithm for the “rolling 6” Design**

Subjects Enrolled a	Number of Subjects and DLT Status		Next Enrollment Dose Level ( $\text{g/m}^2$ per day)		
	Subjects with DLT	Subjects without DLT b	Current Dose level $1.0 \text{ g/m}^2$ per day	Current Dose level $2.0 \text{ g/m}^2$ per day	Current Dose level $1.5 \text{ g/m}^2$ per day
2	0,1 2	0,1,2 0	1.0 Stop c	2.0 1.5	1.5 MTD=1.0
3	0,1 0 ≥2	0,1,2 3 Any	1.0 2.0 Stop c	2.0 2.0 1.5	1.5 1.5 MTD=1.0
4	0,1 0 ≥2	0,1,2,3 4 Any	1.0 2.0 Stop c	2.0 2.0 1.5	1.5 1.5 MTD=1.0
5	0,1 0 ≥2	0,1,2,3,4 5 Any	1.0 2.0 Stop c	2.0 MTD 1.5	1.5 MTD MTD=1.0
6	0,1 0,1 ≥2	0,1,2,3,4 5,6 Any	Suspend 2.0 Stop c	Suspend MTD 1.5	Suspend MTD MTD=1.0

Note: This algorithm selects  $1.0 \text{ g/m}^2$  as the MTD and stops the entire enrollment once  $1.5 \text{ g/m}^2$  exceeds the MTD. Total number of evaluable subjects at dose level  $1.0 \text{ g/m}^2$  can be as few as 3.

a Subjects complete Cycle 1 and evaluable for DLT, or with pending data, excluding non-evaluable subjects.

b Subjects complete Cycle 1 and evaluable for DLT.

c Dose level  $1.0 \text{ g/m}^2$  exceeds MTD.

Up to 18 evaluable subjects may be enrolled if the intermediate cytarabine dose level ( $1.5 \text{ g/m}^2$  per day) is tested and all 3 dose levels recruit 6 subjects.

Subjects enrolled in the Phase 2 portion of the study will receive sequential administration of DACOGEN and cytarabine with the MTD of cytarabine, determined in Phase 1.

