## 11.9. Study Evaluation Team

A Study Evaluation Team (SET) will be established to review the safety data of the Phase 1 portion of the study to determine dose escalation, dose de-escalation, and the MTD of cytarabine.

The SET consists of the sponsor's statistician and clinician (one of whom will chair the committee) and other members as needed, eg, clinical pharmacologist, safety physician. The SET will also include the lead investigator or designee from each country where the study is being conducted. The SET will convene regularly during the Phase 1 portion of this study to assess DLTs, determine dose escalation or de-escalation, and whether a MTD has been reached for cytarabine under these study conditions. The SET may convene at additional times for data review or any safety-related issues including during Phase 2. Any SET member has the right to request a SET meeting. A medical consultant may be asked to participate in the SET if deemed necessary in the interest of patient safety, upon request from the Sponsor or the investigator in preparation for SET meetings. Decisions on dose escalations or de-escalations, changes in the timing of PK or PD sampling, or other study conduct recommendations, will be made by the SET and documented.

All decisions made by the SET (eg, dose escalation/de-escalation, modification of the administration schedule or regimen) will be documented in a SET decision document and distributed to investigators. The IRB will be notified before implementation of any SET decision, if required. This document template will be provided in the sponsor's instruction manual and retained in the study master file and in the study center's files.

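### The non-hematological DLT has two conflicting current definitions, and choosing one over the other can change the cytarabine MTD

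*Combined protocol and SAP*

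**What the plan says.** The Synopsis (Safety Evaluations) and Section 3.1.1 use the same sentence, which opens "A non-hematological DLT is defined as: any Grade" and goes on to 3 or higher, lasting more than 5 days, or an intolerable Grade 2 toxicity lasting more than 7 days. Neither place requires a link to study drug, and neither excludes any event.

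Section 9.2.2, where DLT is set out as a Phase 1 primary endpoint, differs in two ways:

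- The Grade 3 or higher limb requires a "toxicity possibly, probably or definitely related to study drug that persists for" more than 5 days. The Grade 2 limb has no relatedness condition.
- It adds a list introduced by "The following events are more likely disease-related and, therefore, not considered DLTs". The list covers disseminated intravascular coagulation, tumor lysis syndrome, fever, febrile neutropenia, certain electrolyte disorders, and Grade 3 infections including "infection with unknown neutrophil count, and infection without neutropenia".

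No section says which text governs. For details of the rolling 6 "design and the determination of the MTD are provided in Section 6.3", according to 3.1.1, but Section 6.3 only uses "the number of subjects who had DLTs" as an input to Table 3 and does not define a DLT. Section 11.9 says "The SET will convene regularly during the Phase 1 portion of this study to assess DLTs, determine dose escalation or de-escalation", again without naming a definition.

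Three smaller differences sit beside this one:

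- For the hematological DLT, the Synopsis and 3.1.1 join neutropenia and thrombocytopenia with *or*, while 9.2.2 joins the ANC and platelet conditions with *and*.
- Section 9.5 limits the hematological assessment to responding patients, a limit found in none of the other three places.
- Section 9.2.2 uses the category *definitely related*, but the scale in Section 12.1.2 ends at *very likely*.

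**The concern.** The same clinical event can be a DLT in one section and not in another. The MTD rests on the number of subjects with a DLT by the end of Cycle 1, and finding it is a primary objective of Phase 1. It also fixes the cytarabine dose for Phase 2. Under Section 10.2 a DLT is, in addition, a reason to discontinue that subject's study treatment. The definition therefore affects the dose decision for the cohort, the treatment of the individual child and the regimen whose response rate Phase 2 estimates.

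**Working it through.** **1. The texts side by side (non-hematological limb)**

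| Element | Synopsis and 3.1.1 | 9.2.2 |
|---|---|---|
| Grade 3 or higher, more than 5 days | Counts | Counts only if related to study drug |
| Grade 2, more than 7 days, intolerable | Counts | Counts (no relatedness test) |
| Listed events | None excluded | DIC, tumor lysis syndrome, fever, listed infections and febrile neutropenia, listed electrolyte disorders |

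The excluded events are all graded 3 or 4, so the Grade 2 limbs agree. On the Grade 3 or higher limb, 9.2.2 only removes events. On the non-hematological limb, the DLT count under 3.1.1 is therefore at least as large as the count under 9.2.2.

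**2. Events classified differently**

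- A Grade 3 toxicity lasting 6 days and judged unrelated: DLT under 3.1.1, not under 9.2.2 (relatedness).
- A Grade 3 infection lasting 6 days and judged possibly related: DLT under 3.1.1, not under 9.2.2 (exclusion list). This holds even if the word *toxicity* in 3.1.1 is taken to imply relatedness.

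**3. Effect on Table 3**

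The plan's stated maximum reproduces: 3 levels × 6 subjects = 18 evaluable (2 × 6 = 12 without the intermediate level). The conflict does not alter it. The decisions below take all enrolled subjects as complete.

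| Subjects, DLTs | At 1.0 g/m² | At 2.0 g/m² | At 1.5 g/m² |
|---|---|---|---|
| 2 to 5, with 1 DLT | Stay at 1.0 | Stay at 2.0 | Stay at 1.5 |
| 6, with 1 DLT | Go to 2.0 | MTD | MTD |
| 2 to 6, with 2 DLTs | Stop | Go to 1.5 | MTD=1.0 |

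- *1 to 2 DLTs.* Five accrual rows × 3 levels = 15 combinations, and the decision changes in 15 of 15. Allowing pending subjects gives 1+2+3+4+5 = 15 states per level (1 DLT and at least one completed subject without DLT), or 45 over three levels. Reclassifying one completed subject changes all 45.
- *0 to 1 DLT, all complete.* The decision changes in 5 of 15: 3, 4 and 5 subjects at 1.0; 5 subjects at 2.0; 5 subjects at 1.5.

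**4. Illustration of frequency (assumed rates, not in the documents)**

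Let p be the per-subject DLT rate under 9.2.2 and q the chance of an event that counts only under 3.1.1, independent of the first. The hematological limb is held equal under both texts. The rule examined is at most 1 DLT in 6.

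- Given 1 of 6 under 9.2.2, the chance that 3.1.1 gives 2 or more is 1 − (1 − q)^5. For q = 5%, 10% and 20% this is 22.6%, 41.0% and 67.2%.
- Overall disagreement is P(X ≤ 1 | 6, p) − P(X ≤ 1 | 6, u), with u = 1 − (1 − p)(1 − q). At p = 10%: 0.8857 minus 0.7882, 0.6799 and 0.4644, which is 9.8%, 20.6% and 42.1%.
- Varying p from 5% to 20% gives 7.7–10.3%, 17.9–20.9% and 35.5–42.2%.

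**The case against.** The best defense is that the Synopsis and 3.1.1 are summaries and 9.2.2 is the full definition. Section 3.1.1 sits under an overview heading, and 9.2.2 alone gives blood-count thresholds, marrow cellularity, exclusions and evaluability. On that reading, *toxicity* in the shorter texts already implies a link to treatment. This narrows the relatedness gap but does not close the conflict. The shorter texts are worded as definitions and do not cite 9.2.2, no precedence rule exists, and the exclusion list removes named infections whatever their attribution.

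Second, a single SET assesses DLTs and documents its decisions, so dose decisions that diverge from site to site are less likely than they would be otherwise. That is fair, but the SET is not told which text to use.

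Third, 15 of 15 is a property of any rule with a boundary between 1 and 2. It shows consequence, not likelihood. That also stands.

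Fourth, q has no source, and the at-most-1-of-6 rule does not match Table 3 at 1.0 g/m², where 0 DLTs in 3 completed subjects already escalates. If each subject completes before the next enrolls, the rule at that level is 0 of 3, or 1 of 3 followed by 0 of 3. Disagreement at p = 10% is then 8.2%, 17.6% and 37.0%, somewhat lower than the figures above. Nor can Table 2 supply q. Its febrile neutropenia (34%) and pyrexia (48%) figures carry no grade or duration. They come from subjects aged 60 or older with median exposure of 4.14 months, against a DLT window of at most 42 days. They carry no weight here.

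**Conclusion.** The conflict is real and must be fixed. Current sections of the protocol give two definitions of part of a Phase 1 primary endpoint, and each classifies foreseeable events differently. Following one rather than the other can change the Table 3 decision through a single event: in 15 of 15 combinations at the step from 1 to 2 DLTs, and in 5 of 15 at the step from 0 to 1 with all subjects complete. This rests only on the wording and on Table 3, with no assumed rate. How often it would happen is unknown; the disagreement probabilities are illustrations under assumed p and q. The hematological differences and the *responding patients* limit in Section 9.5 are secondary, and the conclusion does not depend on them.

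**What to change.** Reconcile the Synopsis, 3.1.1, 9.2.2 and 9.5 into one governing DLT definition held in one section. Replace the other versions with cross-references, and state in Section 11.9 that the SET applies only that text. The definition should settle:

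- whether relatedness is required, and for which limbs;
- which events, if any, are excluded;
- which Section 12.1.2 categories count as related;
- whether the ANC and platelet conditions apply jointly or separately;
- whether the hematological DLT is limited to responding subjects.

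The clinical content of each answer is the sponsor's decision.

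The cost is a protocol amendment, with ethics committee approval before implementation under Section 16.2.2, and a re-check of any DLT calls and dose decisions already made against the agreed text. No extra subjects, visits or procedures are needed.

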#### 9.5. Safety Evaluations

The evaluation period for safety will start from the time a signed consent/assent is provided. Toxicity/safety will be determined using National Cancer Institute common terminology criteria for adverse events (NCI-CTCAE) version 4.0.

The primary expected toxicity of cytarabine is severe myelosuppression. In addition rare cases of hypersensitivity and anaphylaxis have been reported after cytarabine dosing as well as “sudden respiratory arrest syndrome” occurring 6 to 12 hours after dosing and tumor lysis syndrome.

In addition to myelosuppression, administration of DACOGEN can cause peripheral edema, pallor, cardiac murmur and hypotension. Fever, fatigue, headache, lethargy and other CNS symptoms may occur. Cough, dyspnea, pneumonia and pharyngitis may be seen as well as mucositis and other side effects associated with myelosuppression and cellular cytotoxicity.

For the purposes of DLT evaluation, Cycle 1 will last until the start of Cycle 2, unless there is no recovery from toxicity within the specified time.

During the conduct of Phase 1 the SET will evaluate the tolerability of the combination until such times as a MTD for cytarabine can be agreed upon. Details regarding the SET are provided in Section 11.9.

During Phase 1, blood counts are to be monitored, but hematological parameters are not used to determine the MTD (ie, low blood counts per se are not considered to be dose-limiting toxicities or serious adverse events) because peripheral blood counts and bone marrow function are compromised in patients with relapsed leukemia. Hematological toxicity will only be assessed in responding patients who have grade 4 neutropenia ( $<0.5 \times 10^9/L$ ) or grade 4 thrombocytopenia ( $<25 \times 10^9/L$ ) due to a hypoplastic marrow at Day 42, in the absence of leukaemia.

During Phase 2 only myelosuppression events that are considered life threatening or result in an admission to hospital would be considered as serious adverse events.

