### **10.2. Discontinuation of Study Treatment (Sequential DACOGEN - cytarabine)**

If a subject's study treatment must be discontinued, the End of Sequential Treatment Visit should be performed however, this will not result in automatic withdrawal of the subject from the study. The subject may, at the discretion of the investigator, receive single agent DACOGEN in the Continuation Phase (see Section 9.1.5), otherwise the subject will enter the Follow-up Phase of the study. The End of Sequential Treatment/End of Treatment Visit and Follow-up visit assessments should be performed as specified in the Time and Events Schedule.

A subject's study treatment should be discontinued if:

- The subject experiences a DLT in the Phase 1 portion of the study
- The investigator believes that for safety reasons (eg, adverse event) it is in the best interest of the subject to discontinue study treatment
- The subject becomes pregnant
- The subject has progressive disease by IWG criteria
- The subject is non-compliant with regard to treatment visits
- The subject has sufficient clinical response, in the opinion of the investigator, to be eligible for transplant

- The subject starts another treatment regimen for AML
- The subject is unable to adhere to the study visit schedule or comply with protocol requirements
- The subject or subject's legal representative, parent, or guardian withdraws consent/assent for study treatment.

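### A related severe toxicity that stops treatment in Cycle 1 and resolves within 5 days is not a DLT, and if the cycle is not completed the subject also drops out of the Table 3 count

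*Combined protocol and SAP*

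**What the plan says.** **DLT definition.** Section 9.2.2 makes a Grade 3 or higher non-haematological event a DLT if it is a "toxicity possibly, probably or definitely related to study drug that persists for" more than 5 days. The other limb is Grade 2 toxicity lasting more than 7 "days and that is intolerable to the patient". The Synopsis and Section 3.1.1 use the same durations, without the wording on relatedness. None of the three has a clause for death or for toxicity that ends treatment. The haematological DLT is failure of marrow recovery judged at Day 42.

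**Who is counted.** Section 9.2.2: "Subjects who do not complete one treatment cycle and do not develop DLT will not be considered evaluable for DLT". Section 6.3, on the Table 3 algorithm: "subjects who are enrolled but are non-evaluable (do not complete Cycle 1 and do not develop DLT) are not counted". Table 3 footnote a restricts the enrolled column to evaluable and pending subjects. Section 6.3 also says that DLT is assessed in subjects who receive at least one cycle.

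**Stopping without a DLT.** Section 10.2 lists a Phase 1 DLT as one reason to stop treatment and, as a separate reason: "The investigator believes that for safety reasons (eg, adverse event) it is in the best interest of the subject to discontinue study treatment".

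**End of Cycle 1.** For DLT purposes, Section 9.5 runs Cycle 1 to the start of Cycle 2. The Phase 2 evaluability rule in Section 9.2.2 treats Cycle 1 treatment as over after Day 13. Section 9.1.1 keeps subjects on the assessment schedule whether or not they finish sequential therapy.

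**The concern.** Each rule is understandable alone. A persistence requirement filters out transient toxicity, and replacing subjects who leave early keeps the denominator informative. Together they make the count depend on the outcome it is meant to measure: a subject can become non-evaluable because of the study drugs' toxicity.

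Take a child with a related Grade 4 event, not on the Section 9.2.2 list of exempt events, whose cytarabine is stopped on Day 10 and whose event settles in 4 days. The event is too short to be a DLT, and the Day 42 marrow criterion is not designed to capture it. If the cycle is regarded as not completed, the child is not counted and the slot reopens. Section 9.5 recognises, as rare, acute cytarabine reactions (hypersensitivity, anaphylaxis, respiratory arrest within hours of dosing), which a persistence test fits poorly.

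The count is the Phase 1 primary endpoint. It determines the MTD of cytarabine, and Phase 2 uses that dose. The error runs in one direction, towards tolerability.

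**Working it through.** **1. Check that Table 3 is read correctly.** Six evaluable subjects per level give 6 × 2 = 12, and 6 × 3 = 18 with the intermediate level, matching Section 11.2. The two worked examples in Section 6.3 also reproduce: {4,0,3} at 2.0 leads to 2.0, and {4,2,any} at 2.0 leads to 1.5. Triples are enrolled (evaluable or pending), with DLT, and completed without DLT.

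**2. Two short exits, no assumed rates.** Five subjects are enrolled at a level. Two leave Cycle 1 with related severe toxicity of 5 days or less, and three complete it without a DLT.

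| Treatment of the two exits | Triple | At 1.0 | At 2.0 |
|---|---|---|---|
| Non-evaluable, not counted | {3,0,3} | escalate to 2.0 | continue at 2.0 |
| Counted as DLTs | {5,2,3} | Stop | go to 1.5 |
| Counted as completers without DLT | {5,0,5} | escalate to 2.0 | MTD |

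The first row also meets the Section 3.1.1 minimum for escalation: three fully evaluable subjects without a DLT. The third row applies if completion is read by time observed or by doses given.

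**3. One short exit.** Suppose six subjects, of whom one has a DLT, one has a short exit and four are clean. With both events counted the triple is {6,2,4}: the level is exceeded. With the exit dropped it is {5,1,4}: Table 3 enrols another subject at the same level. The level passes, at {6,1,5}, only if that replacement completes without a DLT.

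**4. Illustration with assumed rates.** Let p be the true rate of DLT or short treatment-stopping toxicity, and f the share of these events that is dropped. The documents give neither figure.

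Counted rate: q = p(1 − f) / (1 − pf).

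Chance of at most one DLT in six evaluable subjects: (1 − q)⁶ + 6q(1 − q)⁵.

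For p = 0.40 and f = 0, q = 0.40, and the chance is 0.047 + 0.187 = 0.233. For p = 0.40 and f = 0.5, q = 0.20/0.80 = 0.25, and the chance is 0.178 + 0.356 = 0.534.

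| Assumed p | None dropped | A quarter dropped | Half dropped |
|---|---|---|---|
| 20% | 65.5% | 75.8% | 86.3% |
| 33% | 35.8% | 48.8% | 66.1% |
| 40% | 23.3% | 35.1% | 53.4% |
| 50% | 10.9% | 19.1% | 35.1% |

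Table 3 can also leave the 1.0 level after three subjects without a DLT. If the level is judged after three, and expanded to six when one of the three has a DLT, the chance of passing is (1 − q)³ + 3q(1 − q)² × (1 − q)³. At p = 40% this rises from 30.9% to 60.0% when half the events are dropped. The absolute figures differ from those for a fixed six; the direction does not.

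**The case against.** The case on the other side has real force on several points.

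- **Death.** A reader might infer that a related toxicity fatal within 5 days is lost from the count. The documents do not establish this. Grade 3 or higher has no upper limit, and a fatal toxicity does not resolve, so it can fairly be read as persisting and hence as a DLT. The text does not say either way. That reading would settle deaths but leave treatment-stopping events open.
- **Completion.** A child who stops cytarabine but is observed through the cycle might stay in the count, because Section 9.5 defines Cycle 1 by time and Section 9.1.1 continues assessments. Removal from numerator and denominator is therefore not certain. On this reading, however, the child counts as having no DLT, which is less protective.
- **A single exit.** A reader might infer that one dropped event turns two DLTs in six into one in six and an accepted level. It does not: step 3 of the working shows that a further subject is needed first.
- **Oversight.** The events do not vanish from view. Serious ones reach the sponsor within 24 hours (Section 12.2.2). The Study Evaluation Team reviews Phase 1 safety, decides escalation and the MTD, and can meet at any member's request (Section 11.9). This reduces the practical risk. It is still discretion: no section says that such an event enters the Table 3 count.
- **Probabilities.** They rest on assumed inputs. The 53% case implies that 0.40 × 0.5 = 20% of all children have a short treatment-stopping event, and the documents support no such figure. The percentages are not operating characteristics of this design.

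**Conclusion.** The point stands for related severe toxicity that stops treatment in Cycle 1 and resolves within 5 days. Under the written rules such an event is never a DLT. The subject is either left out of Table 3 or, if the cycle is taken as completed, entered as free of DLT. Two such exits among five subjects at the 1.0 level change the decision from Stop to escalate, and that result needs no assumed rate. One exit opens a further slot at the same level.

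The handling of a toxicity that ends in death within 5 days is unstated. This should be recorded as a gap, not as a rule that discards deaths.

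How often this would change the selected level cannot be derived from the documents. The rise from 23% to 53% holds only for an assumed true rate of 40%, half of the events dropped, and exactly six evaluable subjects. Review by the Study Evaluation Team mitigates the problem but does not replace a counting rule for the primary endpoint.

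**What to change.** Reconcile the Synopsis and Sections 3.1.1, 6.3 (with Table 3 footnote a), 9.2.2, 9.5 and 10.2 on these points:

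1. Subjects who leave Cycle 1 because of study-drug-related toxicity or death should not be removed as non-evaluable without first being classified.
2. Define what completing Cycle 1 means for DLT evaluation (time observed, doses given, or both) and use that definition throughout.
3. Have the sponsor's clinicians state how an event cut short by death or by stopping treatment is classified against the persistence wording.
4. List in the Study Evaluation Team decision document every subject removed as non-evaluable, with the reason.

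No DLT threshold, dose or escalation rule is proposed here; those remain clinical decisions for the sponsor.

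The cost is a wording change in these sections and one listing, with no added study procedures. The downside is that the selected cytarabine level may come out lower.
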